Number of Subjects: Approximately 132
Study Centers: Approximately 25 in North America and Europe
Purpose of the Study: To determine the efficacy and safety of AR101 compared with placebo in peanut-allergic children aged 1 to < 4 years.
Study Objectives:
Primary:

Efficacy of AR101 treatment in peanut-allergic subjects aged 1 to < 4 years, assessed by tolerability of specified single doses of peanut protein in a double-blind, placebo-controlled food challenge (DBPCFC)
Secondary:

Safety and tolerability of study treatmentEfficacy of AR101, assessed by tolerability of other specified single doses of peanut protein in a DBPCFCMaximum severity of allergy symptoms in a DBPCFC
Exploratory:

Immunologic changesChanges in control of pre-existing atopic disease (asthma, atopic dermatitis)
Study Design:
This is a phase 3, international, randomized, double-blind, placebo-controlled study of the efficacy and safety of AR101 in peanut-allergic children aged 1 to < 4 years. The study will be conducted at approximately 25 study sites in North America and Europe.
Eligible subjects who develop age-appropriate dose-limiting allergy symptoms after consuming single doses of peanut protein > 3 mg to ≤ 300 mg in a screening DBPCFC will be randomly assigned 2:1 to blinded treatment with AR101 or placebo. Randomization will be stratified by geographic region (North America, Europe).
Subjects will begin initial dose escalation under medical supervision at the study site on day 1 with a stepwise dose escalation of study product (up to 4 single doses of 0.5, 1, 1.5, and 3 mg) administered at 20- to 30-minute intervals as tolerated. Subjects who tolerate the 3 mg dose on day 1 will return on day 2 for a single 1 mg dose. Subjects who tolerate the 1 mg dose with no more than mild allergy symptoms that are not dose-limiting will begin the up-dosing period. Subjects who do not tolerate any dose on day 1 or day 2 will discontinue early from the study.
The up-dosing period will be approximately 6 months (maximum 40 weeks), with dose escalation approximately every 2 weeks. Daily doses of study product during up-dosing will be 1, 3, 6, 12, 20, 40, 80, 120, 160, 200, 240, and 300 mg/day. The first dose of study product at each new dose level will be administered under medical supervision at the study site; the remaining doses at each dose level will be administered daily at home as tolerated. Dose adjustments may be allowed. Subjects who tolerate the 300 mg/day dose for 2 weeks within 40 weeks will begin the maintenance period. Subjects unable to tolerate the 300 mg/day dose for 2 weeks within 40 weeks of up-dosing will discontinue early from the study.
Subjects who begin maintenance treatment will continue daily dosing with study product at 300 mg/day for an overall total of approximately 12 months of treatment, with study site visits every 4 weeks. The duration

of maintenance treatment may vary from a minimum of 12 weeks to a maximum of 24 weeks depending on the up-dosing interval (24-40 weeks). Dose adjustments may be allowed. After the end of maintenance, subjects will have an exit DBPCFC up to a single highest challenge dose of 2000 mg peanut protein (4043 mg cumulative). The 300 mg daily dose of study product must be tolerated for at least 2 consecutive weeks before having the DBPCFC. Subjects who complete both days of the exit DBPCFC will exit (complete) the study. Study treatment assignment will be unblinded for a subject after all major data queries for the subject are resolved. Eligible subjects will have the option to enroll in an open-label, follow-on study to receive AR101 treatment. If the follow-on study is not yet available at the study site, blinded study treatment may continue and the visit schedule will be every 4 weeks until the follow-on study is available. At early discontinuation or study exit, subjects with unresolved adverse events or who had gastrointestinal (GI) adverse events of interest (ie, GI adverse events that result in dose interruption > 7 consecutive days or early discontinuation) will have safety follow-up.

An independent, external data and safety monitoring committee (DSMC) will monitor safety on a periodic basis.

Study Schematic:

- [1] Eligible subjects must have age-appropriate dose-limiting allergy symptoms after consuming single doses of peanut protein > 3 mg to ≤ 300 mg in the screening DBPCFC.
- [2] Subjects with unresolved adverse events or who had gastrointestinal adverse events of interest will have safety follow-up.

DBPCFC, double-blind, placebo-controlled food challenge.

Key Eligibility Criteria:

Subjects must be aged 1 to < 4 years at randomization, have written informed consent from a parent/guardian, provide assent (where required and as appropriate per local requirements), and have sensitivity to peanut, defined as one of the following: no known history of peanut ingestion and serum IgE to peanut of ≥ 5 kUA/L within 12 months before randomization, or a documented history of peanut allergy and a mean wheal diameter on skin prick test (SPT) to peanut of at least 3 mm greater than the negative control (diluent) or serum immunoglobulin E (IgE) to peanut of ≥ 0.35 kUA/L, obtained within 12 months before randomization. Subjects must have age-appropriate dose-limiting allergy symptoms after consuming single doses of peanut protein > 3 mg to ≤ 300 mg in a screening DBPCFC. A palatable vehicle food to which the subject is not allergic must be available for administering study product. Subjects must not have a history of severe or life-threatening anaphylaxis; history of hemodynamically significant cardiovascular or renovascular disease (including uncontrolled or inadequately controlled hypertension); history of

biopsy-confirmed diagnosis of eosinophilic esophagitis (EoE); other eosinophilic GI disease; chronic, recurrent, or severe gastroesophageal reflux disease (GERD); symptoms of dysphagia; recurrent GI symptoms considered clinically significant in the opinion of the investigator; history of a mast cell disorder; have moderate or severe persistent asthma, or mild asthma that is uncontrolled or difficult to control; history of high-dose corticosteroid medication use; history of food protein-induced enterocolitis syndrome (FPIES) within 12 months before screening; recurrent urticaria; history of failure to thrive or any other form of abnormal growth, or developmental or speech delay that precludes age-appropriate communication; or any other condition or reason that may interfere with the ability to participate in the study, cause undue risk, or complicate the interpretation of data, in the opinion of the investigator or medical monitor.

Test Product, Dose, and Mode of Administration:

AR101 consists of peanut flour characterized for quantities of specific peanut allergens and is formulated with bulking and flow agents in graduated doses. AR101 will be provided in pull-apart capsules containing 0.5, 1, 10, 20, or 100 mg peanut protein. AR101 will also be provided as 300 mg peanut protein in foil-laminate sachets. Capsules/sachets will be opened; the contents delivered over an age-appropriate, semisolid, vehicle food; and mixed thoroughly.

The sponsor will supply the AR101 for this study. Trained study site personnel will dispense AR101 to the parent/caregiver as appropriate for the assigned dose level.

Reference Therapy, Dose, and Mode of Administration:

Placebo is formulated with the same inactive ingredients as AR101 and without peanut flour. Placebo containing excipients that are color-matched with the peanut flour will be provided as matching capsules identical to the AR101 capsules. Matching placebo-containing sachets are also provided. Capsules/sachets will be opened; the contents delivered over an age-appropriate, semisolid vehicle food; and mixed thoroughly.

The sponsor will supply the placebo for this study. Trained study site personnel will dispense placebo to the parent/caregiver as appropriate for the assigned dose level.

Duration of Treatment:

The total duration of treatment is approximately 12 months (eg, 48-54 weeks) for each subject.

The end of the study is defined as the last assessment for the last subject in the study.

Statistical Methods:

The statistical methods and data presentations for reporting the study will be described in detail in the statistical analysis plan. No interim analyses are planned.

All efficacy analyses will be conducted using the intent-to-treat (ITT) population, defined as all subjects randomly assigned to study treatment who receive any part of 1 dose of study product. Randomization will be central and treatment allocation will be 2:1 (AR101 or placebo). Randomization will be stratified by geographic region (North America, Europe); at least 30% of subjects are planned to be enrolled in Europe.

The primary and secondary efficacy endpoints are defined by major health authority region (North America and Europe):

Primary Efficacy Endpoint:

- **North America:** The primary efficacy endpoint is the proportion of subjects treated with AR101 compared with placebo who tolerate an at least 600 mg single dose of peanut protein with no more than mild allergy symptoms during the exit DBPCFC.
 - The Farrington-Manning test will be used to test the null hypothesis that the difference in desensitization response rate (AR101-placebo) is equal to 0.15 at the two-sided 0.05 significance level. Desensitization response rates and associated 95% CIs will be presented for each treatment group using exact Clopper-Pearson CIs.
- **Europe:** The primary efficacy endpoint is the proportion of subjects treated with AR101 compared with placebo who tolerate an at least 1000 mg single dose of peanut protein with no more than mild allergy symptoms during the exit DBPCFC.
 - The Farrington-Manning test will be used to test the null hypothesis that the difference in desensitization response rate is 0 at the two-sided 0.05 significance level. Desensitization response

rates and associated 95% CIs will be presented for each treatment group using exact Clopper-Pearson CIs.

Secondary Efficacy Endpoints: The following secondary efficacy endpoints will be evaluated in hierarchical order by region (North America and Europe) if the primary efficacy endpoint analysis is significant at the 0.05 level.

North America

1. Proportion of subjects who tolerate an at least 300 mg single dose of peanut protein with no more than mild allergy symptoms during the exit DBPCFC.
2. Proportion of subjects who tolerate an at least 1000 mg single dose of peanut protein with no more than mild allergy symptoms during the exit DBPCFC.
3. The maximum severity of allergy symptoms after consuming peanut protein during the exit DBPCFC.

Europe

1. Proportion of subjects who tolerate an at least 600 mg single dose of peanut protein with no more than mild allergy symptoms during the exit DBPCFC.
2. Proportion of subjects who tolerate an at least 300 mg single dose of peanut protein with no more than mild allergy symptoms during the exit DBPCFC.
3. The maximum severity of allergy symptoms after consuming peanut protein during the exit DBPCFC.

Safety Endpoints:

All safety analyses will be performed using the safety population, defined as all subjects who receive any randomized study treatment. Safety data will be summarized and listed by treatment received.

Safety data will be collected from signed informed consent and assent (where required) through 14 days after the last dose of study product, or through study exit for subjects receiving AR101 treatment in a follow-on study. Safety follow-up data will be collected for at least 30 days after early discontinuation or study exit for subjects with unresolved adverse events, or for at least 6 months after early discontinuation or study exit for subjects with GI adverse events of interest.

Adverse events will be classified by system organ class and coded to preferred term using the Medical Dictionary for Regulatory Activities (MedDRA). Adverse events will be classified by severity using the Consortium of Food Allergy Research (CoFAR) grading system for allergic reactions, modified European Academy of Allergy and Clinical Immunology (EAACI) guidelines for anaphylaxis, and National Cancer Institute (NCI) Common Terminology Criteria for Adverse Events (CTCAE) for all other adverse events. Adverse events of interest include anaphylaxis, GI adverse events with prolonged dose interruption (> 7 consecutive days) or that result in early discontinuation, accidental and nonaccidental food allergen exposure, severe adverse events, and use of epinephrine.

The safety of AR101 treatment versus placebo will be evaluated by the analysis of the incidence of nonserious and serious adverse events, severity of adverse events, incidence and severity of treatment-related adverse events, incidence of dose modifications, and incidence of early treatment discontinuation due to adverse events and due to chronic or recurrent GI adverse events. Separate summaries will be presented for anaphylaxis, allergic reaction adverse events, use of epinephrine, and accidental and nonaccidental food allergen exposure. Summary statistics will be provided for the Test for Respiratory and Asthma Control in Kids (TRACK), Eczema Area and Severity Index (EASI), and laboratory data if relevant.

Exploratory Endpoints:

Exploratory endpoints will be assessed as follows:

- Change from baseline in peanut-specific and peanut component-specific serum immunoglobulins.
- Change from baseline in mean wheal diameter and mean erythema diameter on SPT to peanut.
- Change from baseline in TRACK and EASI scores.
- Palatability of study treatment, assessed using a palatability survey.
- Proportion of subjects who tolerate a single highest dose of 2000 mg peanut protein (4043 mg cumulative) during the exit DBPCFC.

- Change from baseline in the single highest tolerated dose of peanut protein at the exit DBPCFC.
- Maximum dose of peanut protein reached with no more than mild allergy symptoms at the exit DBPCFC.

Sample Size Considerations:

A sample size of 132 subjects randomly assigned at a ratio of 2:1 to AR101 (88 subjects) or placebo (44 subjects) provides sufficient power to detect a treatment difference for the primary efficacy analysis for each major health authority region (North America and Europe) as follows:

- For North America, the sample size provides 85% power to demonstrate a significantly higher desensitization response rate with AR101 compared with placebo with an at least 15% margin for the primary efficacy endpoint of the proportion of subjects tolerating an at least 600 mg single dose of peanut protein with no more than mild allergy symptoms during the exit DBPCFC. The sample size calculations are based on the Farrington and Manning method for the difference in proportions and assume a type I error of 0.05, 2-sided test, a desensitization rate based on the DBPCFC of 55% in AR101-treated subjects, and a maximum desensitization rate of 15% in placebo-treated subjects, conducted in the ITT population.
- For Europe, the sample size provides > 95% power to demonstrate a significantly higher desensitization response rate with AR101 compared with placebo for the primary efficacy endpoint of the proportion of subjects tolerating an at least 1000 mg single dose of peanut protein with no more than mild allergy symptoms during the exit DBPCFC. The sample size calculations are based on the Farrington and Manning method for the difference in proportions and assume a type I error of 0.05, 2-sided test, a desensitization rate based on the DBPCFC of 50% in AR101-treated subjects, and a maximum desensitization rate of 10% in placebo-treated subjects, conducted in the ITT population.

The desensitization rates used in the sample size calculations account for an estimated 25% of subjects across both treatment groups to drop out or discontinue early from the study; these subjects will not be replaced and will be considered nonresponders.

Guidance on Study Conduct During a Pandemic, Epidemic, or Other Emergency Not Related to the Study:

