4.1 Inclusion Criteria

Each subject eligible to participate in this study must meet all the following criteria:

1. Aged 1 to < 4 years at randomization.
2. Written informed consent from the legal guardian/parent (or both parents where required by local authorities). Provide assent where required and as appropriate per local requirements.
3. Sensitivity to peanut, defined as one of the following:
 - a. No known history of peanut ingestion and has serum IgE to peanut ≥ 5 kUA/L within 12 months before randomization.
 - b. Documented history of physician-diagnosed IgE-mediated peanut allergy that includes the onset of characteristic* signs and symptoms of allergy within 2 hours of known oral exposure to peanut or peanut-containing food, and has a mean wheal diameter on skin prick test (SPT) to peanut of at least 3 mm greater than the negative control (diluent) or serum IgE to peanut ≥ 0.35 kUA/L, obtained within 12 months before randomization.

*Characteristic signs and symptoms of IgE-mediated allergic reactions are generally objective and affect the target organs of skin, GI tract, upper/lower respiratory tract, cardiovascular system, or a combination of target organs as follows:

System	Examples of Symptoms (Sampson, 2014)
Cutaneous	Pruritus, erythema/flushing, urticaria, angioedema, contact urticaria
Ocular	Pruritus, tearing, conjunctival injection, periorbital edema
Upper respiratory tract	Pruritus, nasal congestion, rhinorrhea, sneezing, hoarseness, laryngeal edema
Lower respiratory tract	Cough, wheezing, dyspnea, chest tightness/pain
Gastrointestinal	Oral pruritus, oral angioedema (lips, tongue, or palate), colicky abdominal pain, nausea, emesis, diarrhea
Cardiovascular	Tachycardia, dizziness, hypotension, loss of consciousness/fainting

4. Development of age-appropriate dose-limiting allergy symptoms after consuming single doses of peanut protein > 3 mg to ≤ 300 mg in a screening DBPCFC.
5. A palatable vehicle food to which the subject is not allergic must be available for administering study product.

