10 STATISTICAL METHODS

10.1 Statistical and Analytical Plans

The statistical methods and data presentations for reporting the study will be described in detail in the statistical analysis plan.

Randomization will be central and treatment allocation will be 2:1 (AR101 or placebo). Randomization will be stratified by geographic region (North America, Europe); at least 30% of subjects are planned to be enrolled in Europe.

Data for demographic and baseline characteristics, efficacy, and safety will be summarized by treatment group (AR101 or placebo). Summary statistics will include the mean, number of observations, standard deviation, median, minimum and maximum values for continuous variables, and frequencies and percentages for categorical variables.

Statistical significance is defined as $p < 0.05$ and tests will be 2-sided, unless otherwise specified. CIs will be calculated at the 95% level, reflecting a type I error of 0.05.

Missing values for efficacy variables will not be replaced or imputed; no interpolation or extrapolation will be applied to missing values unless otherwise specified in the statistical analysis plan.

The statistical methods and statistical analysis plan may be affected by a pandemic, epidemic, or other emergency not related to the study as described in [Appendix 3](#).

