10.3 Determination of Sample Size

A sample size of 132 subjects randomly assigned at a ratio of 2:1 to AR101 (88 subjects) or placebo (44 subjects) provides sufficient power to detect a treatment difference for the primary efficacy analysis for each major health authority region (North America and Europe) ([Section 10.5.1](#)).

For North America, the sample size provides 85% power to demonstrate a significantly higher desensitization response rate with AR101 compared with placebo with an at least 15% margin for the primary efficacy endpoint of the proportion of subjects tolerating an at least 600 mg single dose of peanut protein with no more than mild allergy symptoms during the exit DBPCFC. The sample size calculations are based on the Farrington and Manning method ([Farrington, 1990](#)) for the difference in proportions and assume a type I error of 0.05, 2-sided test, a desensitization rate based on the DBPCFC of 55% in AR101-treated subjects, and a maximum desensitization rate of 15% in placebo-treated subjects, conducted in the ITT population.

For Europe, the sample size provides > 95% power to demonstrate a significantly higher desensitization response rate with AR101 compared with placebo for the primary efficacy endpoint of the proportion of subjects tolerating an at least 1000 mg single dose of peanut protein with no more than mild allergy symptoms during the exit DBPCFC. The sample size calculations are based on the Farrington and Manning method for the difference in proportions and assume a type I error of 0.05, 2-sided test, a desensitization rate based on the

DBPCFC of 50% in AR101-treated subjects, and a maximum desensitization rate of 10% in placebo-treated subjects, conducted in the ITT population.

The desensitization rates used in the sample size calculations account for an estimated 25% of subjects across both treatment groups to drop out or discontinue early from the study; these subjects will not be replaced and will be considered nonresponders.

Sample size may be affected by a pandemic, epidemic, or other emergency not related to the study as described in [Appendix 3](#).

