10.5.2 Secondary Efficacy Analyses

Secondary efficacy endpoints will be assessed in hierarchical order by major health authority region (North America and Europe) if the primary efficacy endpoint analysis is significant at the 0.05 level. Each endpoint will be evaluated for statistical significance (2-sided, $p < 0.05$) only if all preceding in the hierarchy and the primary analysis of the primary efficacy endpoint are statistically significant in favor of AR101. This closed testing procedure maintains the overall type I error rate at 0.05. If any of the preceding tests are not significant, the p-value will be displayed for informational purposes only.

North America:

1. The proportion of subjects who tolerate an at least 300 mg single dose of peanut protein with no more than mild allergy symptoms during the exit DBPCFC will be assessed using the ITT population and Farrington-Manning test. Desensitization response rates and associated 95% CIs will be presented for each treatment group using exact Clopper-Pearson CIs. The 95% CI for the treatment difference (desensitization rate for AR101 treatment minus desensitization rate for placebo) will be based on the Farrington-Manning method.
2. The proportion of subjects who tolerate an at least 1000 mg single dose of peanut protein with no more than mild allergy symptoms during the exit DBPCFC will be assessed using the ITT population and Farrington-Manning test. Desensitization response rates and associated 95% CIs will be presented for each treatment group using exact Clopper-Pearson CIs. The 95% CI for the treatment difference (desensitization rate for AR101 treatment minus desensitization rate for placebo) will be based on the Farrington-Manning method.
3. The maximum severity of allergy symptoms after consuming peanut protein during the exit DBPCFC will be assessed by tabulating the number and percentage of subjects in the ITT population by maximum severity of allergy symptoms at the exit DBPCFC and by treatment group. The Cochran-Mantel-Haenszel statistics with equally spaced scores (row mean score differences statistic) stratified by geographic region will be used to test for a treatment difference.

Europe:

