The food challenge will be considered positive if ≥ 1 major criteria or ≥ 2 minor criteria are present.

The food challenge will be considered indeterminate if 1 minor criterion is present at the time the food challenge is stopped (ie, onset of the first minor symptom does not meet the food challenge stopping rules).

The food challenge will be considered negative if both major and minor criteria are absent.

Suggested guidelines for the assessment of severity of specific symptoms of an allergic reaction are provided in Table 3. When multiple symptoms are present, the severity of the most severe symptom will be used to determine whether symptoms are dose-limiting and the challenge dose level is tolerated.

Table 3: Guide for Assessment of Allergic Reaction Symptom Severity by Organ System

Organ System	Mild Symptoms	Moderate Symptoms	Severe Symptoms
Skin	Limited (few) or localized hives, swelling (eg, mild lip edema), skin flushing (eg, few areas of faint erythema) or pruritus (mild, eg, causing occasional scratching)	Systemic hives (eg, numerous or widespread hives), swelling (eg, significant lip or face edema), pruritus causing protracted scratching, more than a few areas of erythema or pronounced erythema	Severe generalized urticaria/angioedema/erythema
Respiratory	Rhinorrhea (eg, occasional sniffing or sneezing), nasal congestion, occasional cough, throat discomfort	Throat tightness without hoarseness, persistent cough, wheezing without dyspnea	Laryngeal edema, throat tightness with hoarseness, wheezing with dyspnea, stridor
Gastrointestinal	Mild abdominal discomfort (including mild nausea), minor vomiting (typically a single episode), and/or a single episode of diarrhea	Persistent moderate abdominal pain/cramping/ nausea, more than a single episode of vomiting and/or diarrhea	Severe abdominal pain/cramping/repetitive vomiting and/or diarrhea
Cardiovascular/ Neurologic	Subjective response (weak, dizzy), or tachycardia	Moderate drop in blood pressure and/or > 20% from baseline, or significant change in mental status	Cardiovascular collapse, signs of impaired circulation (unconscious)

Source: Adapted from Practical Allergy (PRACTALL) guidelines ([Sampson, 2012](#)).

Recommended actions for subjects experiencing allergy symptoms are as follows:

Severe symptoms: All severe allergy symptoms are dose-limiting and indicate that the current dose level of the DBPCFC is positive.

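### The exit-challenge severity test is valid but leaves out screening-challenge severity; prespecifying that adjustment could add a few points of power

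*Combined protocol and SAP*

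**What the plan says.** The Synopsis and Section 10.5.2 list "The maximum severity of allergy symptoms after consuming peanut protein during the exit DBPCFC" as secondary endpoint 3 for North America and again for Europe. For both, Section 10.5.2 gives the same ITT analysis: "The Cochran-Mantel-Haenszel statistics with equally spaced scores (row mean score differences statistic) stratified by geographic region will be used to test for a treatment difference". The endpoint is formally tested at two-sided 0.05, but only after the primary endpoint and two other secondary endpoints have succeeded.

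Reaction severity before treatment is not used in the design either. Section 10.1 states: "Randomization will be stratified by geographic region (North America, Europe); at least 30% of subjects are planned to be enrolled in Europe".

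The baseline value can nevertheless be derived:

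- Inclusion criterion 4 (Section 4.1) requires "Development of age-appropriate dose-limiting allergy symptoms after consuming single doses of peanut protein" at the screening challenge, so every randomised child has a screening reaction.
- Appendix 1 governs both challenges. It supplies one mild/moderate/severe guide (its Table 3) and says that with multiple symptoms "the severity of the most severe symptom will be used to determine whether symptoms are dose-limiting".
- Section 8.7.1 requires events during screening to be documented on a case report form, and Appendix 4 has pretreatment allergy symptoms recorded.
- Section 10.7 already treats the screening challenge as baseline for another exit-challenge outcome, the change in single highest tolerated dose.

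The plan states no power, effect size or screening-exit correlation for the severity endpoint.

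**The concern.** If the severity of a child's reaction at exit is related to its severity at screening, part of the spread in exit severity is predictable before randomisation. A test that ignores the predictor treats that spread as noise. The endpoint can support a formal claim, and the trial has only 132 children at 2:1, so a predictor obtained without extra data collection is worth considering. What is at stake is the precision of the last test in each sequence. No other endpoint is affected.

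**Working it through.** **1. The plan's own power figures.** Section 10.3: "A sample size of 132 subjects randomly assigned at a ratio of 2:1 to AR101 (88 subjects) or placebo (44 subjects"). These concern the primary endpoints; no such figure exists for severity.

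- North America, Farrington-Manning, 55% v 15%, margin 0.15. The restricted estimates under the null are 0.458 and 0.308. Null SE = sqrt(0.458×0.542/88 + 0.308×0.692/44) = 0.0876. Alternative SE = sqrt(0.55×0.45/88 + 0.15×0.85/44) = 0.0756. Power = Φ[(0.40 − 0.15 − 1.96×0.0876)/0.0756] = 85.0% (exact enumeration 85.4%), against 85% stated.
- Europe, 50% v 10%, null difference 0: 99.9%, against more than 95% stated.

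Both reproduce, and neither depends on this point.

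**2. Is chance imbalance a fault in the test?** The SE of a chance difference in mean screening severity is sqrt(1/44 + 1/88) = 0.185 SD. Its effect on the exit comparison is r times that, for example 0.4 × 0.185 = 0.074 SD, and is already inside the test's error rate. Simulated size of the region-only test was 4.7 to 5.5% over latent correlations of 0 to 0.7 (4,000 trials each, standard error about 0.3 points). The test holds its level.

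**3. Analytic gain.** Linear adjustment multiplies the variance by 1 − r². If the region-only test had 80% power, the effect would be (1.960 + 0.842) × 0.185 = 0.517 SD, and adjusted power = Φ[2.802/sqrt(1 − r²) − 1.960].

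| Observed r (assumed) | Variance factor | Power from 80% | Equivalent extra children on 132 |
|---|---|---|---|
| 0.1 | 0.99 | 80.4% | 1 |
| 0.2 | 0.96 | 81.6% | 6 |
| 0.3 | 0.91 | 83.6% | 13 |
| 0.4 | 0.84 | 86.4% | 25 |
| 0.5 | 0.75 | 89.9% | 44 |

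**4. Simulation of the test itself.** None of the following assumptions comes from the documents. Placebo exit severity is none 5%, mild 30%, moderate 45%, severe 20%. Screening severity is mild 35%, moderate 50%, severe 15%. Europe has 30% of children, the shift is 0.55 latent SD, and all 132 have exit data. Here r is the correlation on the latent scale. In a companion simulation with similar class shares, a latent 0.5 gave about 0.39 between the observed categories, so these gains are smaller than those in step 3 at the same nominal r.

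| Latent r | Region only | Region × severity, six strata | Region + one ordered severity score |
|---|---|---|---|
| 0 | 79.6% | 77.6% | loss of no more than about 1 point |
| 0.2 | 78.1% | 77.7% | no useful gain |
| 0.4 | 77.8% | 82.6% | 83.2% |
| 0.5 | 78.8% | 84.1% | 84.8% |

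For the ordered score the gains are 83.2 − 77.8 = 5.4 and 84.8 − 78.8 = 6.0 points. Size stayed near 5%.

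**5. Missing exit challenges.** Section 10.3 expects 25% to leave early. With 25% of exit severities missing, six strata against region only gave 64% v 66% at r = 0, 64% v 64% at 0.2 and 69% v 66% at 0.4 (simulation error about 0.7 points).

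**6. Sparse strata.** Under these assumptions a given placebo child falls in the Europe-severe stratum with exit data with probability 0.30 × 0.15 × 0.75 = 0.034. That is 44 × 0.034 = 1.5 expected children, and no such child in (1 − 0.034)^44, about 22%, of trials. In those trials the AR101 children in that stratum add nothing to the test.

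**7. Large effect.** With 25% missing and r = 0.4, a 1.0 SD shift gave 98.9% for region only and 99.3% for six strata.

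**The case against.** The strongest reply is that the planned test is valid and prespecified, and that the benefit of changing it is unknown and could be negative.

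Several features may make the correlation modest. Screening stops at 300 mg and exit goes to 2000 mg (Section 9.2). Every child must react at screening, which restricts the range. A challenge is halted once stopping criteria are met, so recorded severity partly reflects when it was stopped. The same physician assesses screening and exit only where practicable (Appendix 1). Two thirds of the children receive desensitising treatment between the challenges. All of this stands, and it is why the gain can only be stated conditionally.

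The six-stratum form has costs of its own. With 25% missing and a latent correlation of 0.4 on placebo but 0 on AR101, it gave 63% against 66% for region only. This stands against six strata and is the reason to prefer a single ordered score.

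The 0.55 SD effect was also chosen where adjustment can show. The plan's 55% v 15% on the 600 mg endpoint corresponds to Φ⁻¹(0.55) − Φ⁻¹(0.15) = 0.126 + 1.036 = 1.16 latent SD. If the severity effect were that large, power would be near its ceiling either way. The documents do not say how large it is.

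Section 10.5.2 leaves full details to the SAP, and no separate SAP text was available for this review. The point therefore concerns the test as the protocol states it. That deferral does not change the stated test.

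Two stronger readings are tempting. A reader might infer that chance imbalance in screening severity biases a formally tested endpoint. It does not: under randomisation it is random error that the 5% level already covers. A reader might also infer that power is definitely being given away. That needs a correlation of about 0.4 or more, for which the documents offer no evidence.

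**Conclusion.** The point holds as a matter of precision, at the level of a worthwhile refinement. The stated test for endpoint 3 in both hierarchies is valid at 5% and omits a baseline value that can be derived for every randomised child.

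The size is conditional on a screening-exit correlation that must be assumed. The gain is about nil at 0.2 or below. It is roughly 3 to 6 points of power at 0.4 to 0.5 when unadjusted power is 65 to 80%. It is little if the effect is large. These figures rest on assumed severity distributions and a 0.55 SD shift. The conclusion that the planned test keeps its level does not depend on them.

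**What to change.** In Section 10.5.2, items North America 3 and Europe 3, and in the SAP, prespecify before unblinding that the severity comparison is adjusted for geographic region and for maximum severity at the screening challenge, entered as a single ordered score. A covariate-adjusted mean-score test keeps the planned equally spaced scoring; a proportional-odds model with both terms is an alternative. Avoid six region-by-severity strata. If a stratified CMH test is preferred, collapse screening severity to mild v moderate or worse. State how screening maximum severity is derived from the recorded symptoms, and tabulate exit by screening severity by arm. If the team keeps the region-only test, one sentence of justification in the SAP is enough.

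The cost is one clause and no new data collection. The statistical downside is about 1 point of power if screening and exit severity are uncorrelated, against up to about 2 points with six strata. The timing matters because a covariate added after unblinding would look data-driven.
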